# 4.3. Justification for Dose

Two doses of belcesiran will be evaluated in this study: 210 mg and 50 mg. No safety concerns have been identified by the SRC or DSMC who reviewed all available DCR-A1AT-101 data prior to dosing the first patient in DCR-A1AT-201. Both doses selected for this study are within the dose range tested in DCR-A1AT-101 and are expected to be safe and well-tolerated. In addition, the NOAEL plasma exposure observed in the pivotal repeat-dose toxicity studies provides adequate safety margin for the expected exposure at these doses (at least 23-fold to the

high dose proposed in this study). Details on clinical safety data from DCR-A1AT-101 and nonclinical toxicology studies are provided in the DCR-A1AT Investigator Brochure.

A PK/PD modeling and simulation analysis was performed using all available PK and PD (serum AAT protein levels) data from DCR-A1AT-101 including data up to EOT for 12 mg/kg dose and all available data from C-F/U period. The adequacy of models in describing the available data and the predictive performance of the final model were assessed using pre-specified goodness-of-fit criteria. Based on the final PK/PD model, simulations of serum AAT profiles were performed to inform the dosing regimen for this study. A dataset of 1000 virtual adult subjects was created by sampling the demographics for these virtual subjects from the National Health and Nutrition Examination Survey (NHANES; http://wwwn.cdc.gov/nchs/nhanes/search/ nhanes\_continuous.aspx.), with age range of 18 to 65 years and weight range of 41 to 199 kg (median weight of 77.5 kg). Various dosing regimens, including weight-based dose and fixed dose with different dosing intervals, were evaluated. The simulations over the wide range of weight indicated that weight-based and equivalent fixed-dose regimens would result in similar reductions in serum AAT. Given similar predicted PD responses, a fixed-dose regimen is preferred over the weight-based regimen for ease in dose administration.

The 210 mg q4w dosing regimen was selected to target a near-maximal PD response. From the simulations, the mean reduction in serum AAT was predicted to be approximately 82% by Week 24 (90% prediction interval [PI]: -59.1% to -98.8%). A lower dose of 50 mg q4w was included to better characterize the dose-exposure-response relationship of belcesiran and its safety profile over a range of serum AAT reduction. Following the administration of 50 mg q4w, the mean reduction in serum AAT was predicted to be approximately 65% (90% PI: -44.5% to -82.4%) by Week 24. Simulations predicted a serum AAT reduction of at least 50% by Week 24 in about 90% of the participants receiving 50 mg q4w dose, suggesting a 50% reduction in hepatic AAT production. It has been shown that adults with the SERPINAI PiMZ genotype, which leads to an approximately 50% reduction in hepatic Z-AAT production, have lower levels of serum transaminases, fewer AAT inclusions in liver, and lower liver stiffness than adults with the PiZZ genotype, although higher than adults without the PiZ variant (Schneider et al, 2020). Therefore, the 50 mg q4w dose, which is predicted to reduce hepatic Z-AAT production (and hence the downstream serum Z-AAT) by at least 50% in the majority of study participants with AATLD, may offer some clinical benefits to most of the participants receiving this dose while expanding the range of PD response for dose-exposure-response characterization.

Monthly dose frequency has been selected for Cohorts 1 and 2 to maximize potential PD response. The first 6 months dosing in Cohort 3 will also be monthly after which patients will shift to quarterly dosing. The rationale for exploring an alternative dosing regime is out of consideration for patient burden. For the high dose explored, simulations suggest that reducing dose frequency after steady state would only have a minor effect on the PD response.

In summary, the two belcesiran doses included in the clinical protocol (210 mg and 50 mg) are predicted to result in a range of PD response that would allow for adequate characterization of belcesiran dose-exposure-response in patients with AATLD.

# 4.4. End of Study Definition

A participant is considered to have completed the study if he or she has completed all phases of the study (including F/U), including the last visit or the final scheduled procedure shown in the SoAs (Section 1.3).

The end of the study is defined as the completion of the final database lock.

# 5. STUDY POPULATION

# 5.1. Inclusion Criteria

Participants are eligible to be included in the study only if all of the following criteria apply:

### Age

1. Age 18 to 75 years, inclusive, at the time of signing the ICF.

### Type of Participant and Disease Characteristics

- 2. Documented diagnosis of PiZZ-type AATD, confirmed by genotyping. Historical genotyping data may be used, if available.
- 3. AATLD, with a liver fibrosis score categorized as F1, F2, F3, or F4 in the METAVIR scoring system, documented by liver biopsy during Screening.
- 4. Post-bronchodilator  $FEV_1 > 45\%$  of predicted at Screening.
- 5. Participants receiving augmentation therapy on a regular basis and intending to continue augmentation therapy during the study are eligible to participate.
- 6. eGFR at Screening  $\geq$  60 mL/min normalized to 1.73 m^2 BSA.
- 7. Non-smokers (defined as having not smoked cigarettes daily for at least the preceding 12 months) with current non-smoking status confirmed by urine cotinine at Screening AND any previous smoking history prior to 12 months must be < 15 pack years, including use of e-cigarettes. Participants may be on nicotine replacement (patch or gum). A positive urine cotinine result due to nicotine replacement is acceptable for enrollment at the discretion of the Investigator.

### Sex

8. Male or female

### Male participants:

A male participant with a partner of childbearing potential must agree to use contraception, as detailed in Section 10.4.2, during the treatment period and for at least 12 weeks after the last dose of study intervention and refrain from donating sperm during this period.

### Female participants:

A female participant is eligible to participate if she is not pregnant (see Section 10.4.2), not breastfeeding, and at least one of the following conditions applies:

Not a woman of childbearing potential (WOCBP) as defined in Section 10.4.1

OR

A WOCBP who agrees to follow the contraceptive guidance in Section 10.4.2 during the treatment period and for at least 12 weeks after the last dose of study intervention.

Contraceptive use should be consistent with local regulations regarding the methods of contraception for those participating in clinical studies.

### **Informed Consent**

9. Capable of giving signed informed consent, which includes compliance with the requirements (including consent to undergo paired liver biopsies) and restrictions listed in the ICF and in this protocol.

# 5.2. Exclusion Criteria

Participants are excluded from the study if any of the following criteria apply:

### **Medical Conditions**

- 1. Any condition which, in the investigator's opinion might jeopardize participant's safety or compliance with the protocol.
- 2. History of chronic liver disease other than non-alcoholic fatty liver disease from any cause other than PiZZ-type AATD. Diagnostic testing exclusions are defined in the Diagnostic Assessments section below.
- 3. Child-Pugh Score B or C or a previous hepatic decompensation event.
- 4. History of one single severe exacerbation of underlying lung disease in the year prior to randomization.

A severe exacerbation is defined as an exacerbation that requires hospitalization or a visit to the emergency room.

- 5. History of rapid decline in pulmonary function, as assessed by the Investigator.
- 6. Known or suspected abuse of drugs in the opinion of the Investigator.
- Known or suspected excessive consumption of alcohol (≥ 21 units of alcohol per week in men and ≥ 14 units of alcohol per week in women; where a "unit" of alcohol is equivalent to a 12-ounce beer, 4-ounce glass of wine, or 1 ounce shot of hard liquor as defined by the World Health Organization).
- 8. Any of the following: myocardial infarction, stroke, classification of heart failure New York Heart Association (NYHA) Class IV, hospitalization for unstable angina pectoris or transient ischemic attack within the past 90 days prior to the day of screening (V2A) and between screening and randomization.
- 9. History of malignancy, unless the malignancy (other than hepatocellular or lung cancer) has been in complete remission off chemotherapy and without additional medical or surgical

interventions within the preceding 5 years, or unless the malignancy has been an adequately treated skin cancer (other than melanoma) or, superficial bladder tumor, or in situ cervical cancer in the preceding 1 year.

### **Prior/Concomitant Therapy**

- 5. Use of an RNAi drug at any time.
- 6. History of one or more of the following reactions to an oligonucleotide-based therapy:
  - a. severe thrombocytopenia (platelet count < 100,000/ mm^3)
  - b. hepatotoxicity, defined as ALT or AST  $> 3 \times$  ULN and total bilirubin  $> 2 \times$  ULN or INR > 1.5
  - c. severe flu-like symptoms leading to discontinuation of therapy
  - d. localized skin reaction from the injection (graded severe) leading to discontinuation of therapy
  - e. coagulopathy/clinically significant prolongation of clotting time

### **Prior/Concurrent Clinical Study Experience**

7. Participation in any clinical study in which they received an IMP within 4 months (or 5 times the half-life, whichever is longer) before Screening.

#### **Diagnostic assessments**

8. AST and  $ALT > 5 \times ULN$  at Screening

For individuals with any serum aminotransferase elevation  $> 2 \times ULN$ , autoimmune hepatitis should be ruled out through the appropriate screening tests, which may include total IgG or gamma-globulin levels and/or serologic markers (i.e., antinuclear antibodies, anti-smooth-muscle antibodies at a titer of at least 1:40, anti-liver/kidney microsomal-1 antibodies, anti-liver cytosol antibody [anti-LC 1], or antisoluble liver/liver pancreas [anti-SLA/LP] antibodies).

- 9. ALP  $2 \times$  ULN at Screening.
- 10. Serum AFP value > 100 ng/mL at Screening.

If AFP at screening is > ULN but < 100 ng/mL, the participant is still eligible if an appropriate hepatic imaging study reveals no lesions.

- 11. Positive screening for antimitochondrial antibodies (only required if primary biliary cholangitis is suspected).
- 12. Platelets < 100,000/mm^3 at Screening
- 13. INR  $> 1.6 \times$  ULN at Screening

14. Positive screening for HBsAg, HCV antibodies, or HIV1 and 2 antibodies. If a participant has been tested in the past 3 months, medical record documentation of this testing can be used for eligibility.

NOTE: In participants with previous treatment for hepatitis C with direct-acting HCV medication and seropositivity for HCV, or in participants with prior infection and spontaneous resolution, HCV RNA must be undetectable (at least 2 negative HCV RNA tests at least 12 weeks apart), and the HCV infection must have been resolved or cured > 3 years prior to enrollment.

# 5.3. Lifestyle Considerations

### 5.3.1. Meals and Dietary Restrictions

During this study, participants will be asked to:

Abstain from heavy drinking throughout the study period, for example, no more than ≥ 21 units of alcohol per week in men and ≥ 14 units of alcohol per week in women (4 units per day for men and 3 units per day for women); where a "unit" of alcohol is equivalent to a 12-ounce beer, 4-ounce glass of wine, or 1 ounce shot of hard liquor as defined by the World Health Organization. Social drinking is allowed.

### 5.3.2. Activity

During this study, participants will be asked to:

- Abstain from strenuous exercise for 48 hours before each blood collection for clinical laboratory tests. Participants may participate in light recreational activities (e.g., walking at a pace < 3 miles per hour, shopping, watering plants) in that 48-hour time period.

- Plan to undertake no significant changes in exercise levels from the 48 hours prior to Day 1 until completion of the study, including F/U.

# 5.4. Screen Failures

Screen failures are defined as participants who consent to participate in the clinical study but are not subsequently randomly assigned to the study intervention/entered in the study. A minimal set of screen failure information is required to ensure transparent reporting of screen failure participants, to meet the CONSORT publishing requirements, and to respond to queries from regulatory authorities. Minimal information includes, but are not limited to, demography, screen failure details, eligibility criteria, and any SAE.

Individuals who do not meet the criteria for participation in this trial (screen failure) may be rescreened once, at the discretion of the Investigator.

Rescreened participants will be assigned the same participant number as originally assigned preceded by the number "9."

### 5.4.1. Screening Tests Required during the Rescreening Period

If a participant undergoes rescreening after being deemed a screen failure, the following screening assessments do not need to be repeated as part of the rescreening visit.

- Liver biopsy performed within 180 days (if the participant screen failed before a biopsy was performed, the liver biopsy must be collected as part of rescreening)
- PiZZ genotyping
- Viral serology (documented results within 3 months)
- Pulmonary X-ray (initial Screening pulmonary X-ray within 3 months of rescreening)
- FibroScan (initial Screening FibroScan within 30 days of the start of rescreening)
- MRE (initial Screening MRE within 30 days of the start of rescreening) (Cohort 1 & 2 only)
- Spirometry (initial Screening Spirometry within 30 days of the start of rescreening)
- DLCO (initial Screening DLCO within 30 days of the start of rescreening)
- Serum biomarkers (initial Screening serum biomarkers collected within 30 days of rescreening)

Any assessment not listed above must be performed again as part of the rescreening procedures.

# 6. STUDY INTERVENTION

Study intervention is defined as the investigational intervention, or placebo, intended to be administered to a study participant according to the study protocol.

# 6.1. Study Intervention Administered

Belcesiran is supplied as a solution of the drug substance (belcesiran sodium) in water for injection. The molecular mass of the sodium salt and free acid of the drug substance is 22286.2 Da and 21033.3 Da, respectively. The manufactured drug substance can be isolated only as a salt. As such, nonclinical and early clinical doses were expressed in terms of the sodium salt form of the drug substance. However, the United States Pharmacopeia 2013 "Salt Policy" specifies that when the active ingredient in a drug product is a salt, the strength should be expressed in terms of the active moiety rather than salt strength equivalent. For belcesiran, the sodium salt provides an additional 5.6% mass to the free acid. As such, the table below provides drug product concentrations and doses expressed in both the sodium salt and equivalent free acid ("active moiety") weights.

Arm Name	Active		Placebo
Intervention name	belcesiran		0.9% saline for injection
Intervention type	Drug		Drug
Dose formulation	solution for injection		solution for injection
	Sodium salt	Free acid	
Drug product concentration	185 mg/mL	175 mg/mL	n/a
Route of administration	SC injection (thigh or abdomen)		SC injection (thigh or abdomen)
IMP or NIMP	IMP		n/a
Sourcing	Provided centrally by the Sponsor or designee		Provided locally by the trial site
Packaging and labeling	Belcesiran will be provided in vials. Each vial will be labeled as required per country.		n/a

Abbreviations: IMP: investigational medicinal product; n/a: not applicable; NIMP: non-investigational medicinal product; SC: subcutaneous.

### 6.1.1. Dose Level

Participants will receive belcesiran (or matching placebo) at a fixed dose of 210 mg in Cohorts 1 and 2 or a fixed dose of either 50 mg or 210 mg in Cohort 3. Cohorts 1 and 2 will be dosed monthly and Cohort 3 will be dosed monthly for the first 6 months and then quarterly thereafter. Participants in Cohort 1 will receive up to 13 doses, participants in Cohort 2 will receive up to 17 doses, and participants in Cohort 3 will receive 13 doses.

# 6.2. Preparation/Handling/Storage/Accountability

The Investigator or designee must confirm appropriate temperature conditions have been maintained during transit and storage at the site for all study intervention received, and any discrepancies are reported and approved by the Sponsor before the administration of the study intervention.

Only participants enrolled in the study may receive study intervention, and only authorized site staff may prepare or administer study intervention. All study intervention must be stored in a secure, environmentally controlled, and monitored (manual or automated) area per the labeled storage conditions with access limited to authorized site staff.

The authorized site staff are responsible for study intervention accountability, reconciliation, and record maintenance (i.e., receipt, reconciliation, and final disposition records).

Further guidance and information for the final disposition of unused study interventions are provided in the Pharmacy Manual.

Belcesiran is to be stored at 2°C to 8°C (inclusive). Belcesiran should be allowed to warm to room temperature for approximately 1 hour (but no more than 4 hours) before administration.

Further guidance and information regarding study interventions are provided in the Pharmacy Manual.

# 6.3. Measures to Minimize Bias: Randomization and Blinding

The study is a randomized, placebo-controlled, double-blind study, where the Investigator and the study participants are blinded to IMP and placebo. All sites will have unblinded staff responsible for preparing IMP. A subset of the Sponsor's study team will be unblinded. Details of unblinding, including the list of unblinded Sponsor team members, will be captured in the Study Specific Blinding Plan.

All participants will be centrally assigned to randomized study intervention using an IVRS/IWRS. Before the study is initiated, directions for the IWRS will be provided to each site.

Investigators will remain blinded to each participant's assigned study intervention throughout the course of the study. In order to maintain this blind, the unblinded site staff will be responsible for the preparation and dispensation of all study intervention and will endeavor to ensure that there are no differences in the time taken to dispense the study intervention following randomization. Additionally, the unblinded site staff will affix a translucent label over the syringe(s) to mask the contents.

The unblinded study monitor and any auditors present in the event of a Quality Assurance or a competent authority audit will be allowed access to unblinded study intervention records at the site(s) to verify that randomization/dispensing has been done accurately and per protocol and the Pharmacy Manual.

In case of an emergency, the Investigator has the sole responsibility for determining if unblinding of a participant's treatment assignment is warranted. Participant safety must always be the first consideration in making such a determination. If a participant's treatment assignment is unblinded, the Medical Monitor must be notified within 24 hours after breaking the blind. The date and reason that the blind was broken must be recorded in the source documentation.

Potentially unblinding study results, such as the serum AAT protein concentrations, will not be shared with blinded study participants and site personnel during the treatment period.

# 6.4. Study Intervention Compliance

Study intervention will be administered at the investigational site or home (after the first dose) if the participant is unable to come to the study site. The planned dose, actual administered dose, and injection date and time will be recorded in the source documentation.

# 6.5. Concomitant Therapy

Any medication or vaccine (including OTC or prescription medicines, vitamins, and/or herbal supplements) that the participant is receiving within 30 days prior to Screening or receives during the study treatment period must be recorded along with:

- o Reason for use
- o Dates of administration including start and end dates
- o Dosage information including dose and frequency

The Medical Monitor should be contacted if there are any questions regarding concomitant or prior therapy.

### 6.5.1. Augmentation Therapy

Study participants who are receiving augmentation therapy prior to study entry should continue their augmentation therapy on a regular basis for the duration of the study.

For study participants who are not receiving augmentation therapy prior to study entry, augmentation therapy is available in case of a clinically significant worsening in lung function at the discretion of the investigator during the entire trial. Only doctors with augmentation therapy experience should make the decision to initiate the treatment. The date, time, and dosage regimen of intravenous purified AAT administration must be recorded.

### 6.5.2. Vaccinations

Where possible, to allow discernment of AEs related to the administration of a vaccine from those related to administration of study intervention, vaccines should not be administered in the 7 days prior to or following scheduled administration of study intervention.

### 6.6. Dose Modification

No dose modifications for individual participants will be allowed.

# 6.7. Intervention after the End of the Study

Upon completion of the study, Investigators will discuss care options with participants.

# 7. STUDY INTERVENTION DISCONTINUATION AND PARTICIPANT DISCONTINUATION/WITHDRAWAL

# 7.1. Discontinuation of Study Intervention

Treatment of a participant may be discontinued at any time during the trial at the discretion of the investigator for safety, behavioral, compliance or administrative reasons. Efforts must be made to have participants, who discontinue trial product, continue in the trial to evaluate safety and serum AAT protein concentrations. Participants must be educated about the continued scientific importance of their data, even if they discontinue trial product. Data to be collected at the time of intervention discontinuation and follow-up and for any further evaluations that need to be completed are outlined in the SoA (Section 1.3). Only participants who withdraw consent will be considered as withdrawn from the trial.

### 7.1.1. Stopping Rules for Individual Participants

Discontinuation of treatment can be decided by either the Investigator or the participant. Participants who discontinue trial product should continue with the scheduled visits and assessments. If the participant does not wish to attend the scheduled clinic visits, efforts should be made to have visits converted to phone contacts. However, all efforts should be made to have the participant attend the visits at week 24, 48 and 96, as applicable.

The trial product must be discontinued, if any of the following applies for the participant:

1. Decline in Pulmonary Function (see Section 7.1.1.1)

2. Abnormal liver blood parameters indicating DILI (see Section 7.1.1.2)

3. Pregnancy/ Intention of becoming pregnant

4. Simultaneous use of an approved or non-approved investigational medicinal product in another clinical trial

5. Safety concerns as judged by the Investigator

Participants meeting any of the above treatment discontinuation criteria are allowed to resume trial product, if the criterion is no longer met.

For Germany: please also see country-specific requirements in Section 10.5.

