#### Number of Participants:

Up to a total number of 16 participants will be enrolled in Cohorts 1 and 2. A total of 30 participants will be enrolled in Cohort 3.

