### 7.1.1.2. Drug-Induced Liver Injury Monitoring

### For Participants with Normal Liver Biochemistries at Baseline

Study intervention will be discontinued when a participant meets one of the conditions outlined below (from Guidance for Industry-Drug Induced Liver Injury: Premarketing Clinical Evaluation [FDA, 2009]) or if the Investigator believes that it is in the best interest of the participant. Safety laboratories will be monitored by a central laboratory in real time with potential drug-induced liver injury (DILI) alerts sent to the Investigator.

- $\circ \quad \text{ALT or AST} > 8 \times \text{ULN}$
- ALT or AST >  $5 \times$  ULN for more than 2 weeks
- ALT or AST  $> 3 \times$  ULN and (total bilirubin  $> 2 \times$  ULN or INR > 1.5)
- $\circ$  ALT or AST > 3 × ULN with the appearance of fatigue, nausea, vomiting, right upper quadrant pain or tenderness, fever, rash, and/or eosinophilia (> 5%)

Participants should be monitored at each study visit and instructed to call the Investigator for new or worsening symptoms of clinical hepatitis. Both symptoms and calls should be documented in source notes.

NOTE: Any elevation in an LFT leading to discontinuation of study intervention must be at least possibly related to the investigational drug, and other potential causes (e.g., strenuous exercise, use of concomitant medication) must have been excluded.

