### Assessments in Case of Increased Levels of Liver Blood Parameters

For all such events listed above repeated testing must occur within 48 to 72 hours and work up for competing etiologies must be performed including:

- Complete liver profile including ALT, AST, alkaline phosphatase, conjugated bilirubin, total bilirubin and INR. Hereafter repeat testing should be done 2 to 3 times weekly. If close monitoring is not possible the trial product should be discontinued. The frequency of repeat testing can decrease to once a week or less if abnormalities stabilize and the participant is asymptomatic.
- A detailed history of symptoms and prior or concurrent diseases.
- History of concomitant drug use (including non-prescription medications and herbal and dietary supplement preparations), alcohol use, recreational drug use, and special diets.
- Ruling out acute viral hepatitis (including hepatitis A, B, C and E); autoimmune or alcoholic hepatitis; hypoxic/ischemic hepatopathy; and biliary tract disease.
- Obtaining a history of exposure to environmental chemical agents.

Trial product can be restarted if an alternative etiology is definitively identified, and liver blood parameters have returned to pre-event levels.

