# 8. STUDY ASSESSMENTS AND PROCEDURES

The timing of study procedures is summarized in the SoAs (Section 1.3). Protocol waivers or exemptions are not allowed.

Immediate safety concerns should be discussed with the Medical Monitor upon occurrence or awareness to determine if the participant should continue or discontinue study intervention.

Adherence to the study design requirements, including those specified in the SoAs (Section 1.3), is essential and required for study conduct.

Informed consent must be obtained before any trial related activity (Section 10.1.3)

All screening evaluations must be completed and reviewed to confirm that potential participants meet all eligibility criteria. The Investigator will maintain a screening log to record details of all participants screened and to confirm eligibility or record reasons for screening failure, as applicable.

The maximum amount of blood drawn from each participant at any visit (including PK, PD, and safety laboratory testing) will not exceed:

o 132 mL

The total amount of blood collected (including PK, PD, and safety laboratory testing) will not exceed:

- o 480 mL in 28 days or
- o 550 mL in 8 weeks

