1 INTRODUCTION

The purpose of this Statistical Analysis Plan (SAP) is to provide a description of the statistical methods to be implemented for the analysis of study data from protocol DCR-A1AT-201, “A Phase 2, Randomized, Double-blind, Placebo-controlled Study Investigating Safety, Tolerability, Pharmacokinetics and Pharmacodynamics of Two Dose Levels of Belcesiran in Patients with Alpha-1 Antitrypsin Deficiency-Associated Liver Disease”. The SAP will be finalized prior to the final database lock. Any deviations from the SAP after database lock will be documented in the final Clinical Study Report (CSR).

The SAP reflects the planned study design as per the latest version of the protocol; however, the Sponsor made the decision to stop the trial prior to the enrollment of Cohort 3 subjects and prior to the completion of the planned study procedures for Cohorts 1 and 2 participants. Cohort 3 and related activity plan will be cancelled. Therefore, the available safety, AAT and biopsy data from Cohort 1 and Cohort 2 will be analyzed for the CSR purpose and there is no analysis planned for Cohort 3.

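### Protocol 7.1.1 and 7.1.1.2 set different conditions for restarting drug after a DILI stop, and no text says which governs

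*Protocol*

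**What the plan says.** Protocol Section 7.1.1 names five criteria that require trial product to be stopped. Criterion 2 is abnormal liver tests pointing to DILI, with a pointer to Section 7.1.1.2. After the list comes one resume rule: "Participants meeting any of the above treatment discontinuation criteria are allowed to resume trial product, if the criterion is no longer met". It has a single condition and covers all five criteria.

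Section 7.1.1.2 gives the liver thresholds, separately for participants with normal liver tests and with raised transaminases at baseline. Its last subsection, on assessments when liver parameters rise, applies to both groups: "For all such events listed above repeated testing must occur within 48 to 72 hours and work up for competing etiologies must be performed". That subsection closes with a restart rule of its own: "Trial product can be restarted if an alternative etiology is definitively identified, and liver blood parameters have returned to pre-event levels". This rule has two conditions, joined by *and*.

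A NOTE under the normal-baseline thresholds bears on how the second rule works. It says that an elevation leading to discontinuation must be at least possibly drug-related, "and other potential causes (e.g., strenuous exercise, use of concomitant medication) must have been excluded".

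**The concern.** A site holding a participant off drug after a liver event needs one answer to one question: may the next dose be given? Section 7.1.1 says yes once the criterion has cleared. Section 7.1.1.2 asks for more. The pointer in criterion 2 tells the site where the stopping thresholds are; it does not say that the restart rule there displaces the general one.

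The stake is re-exposure. Participants have F1 to F4 liver fibrosis, the drug acts in the liver, and Section 2.3.4 names liver test elevation among the key potential risks. An unexplained, possibly drug-related elevation that settles off drug is the case in which a restart rule matters most, and it is the case in which the two sections part.

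**Working it through.** The plan gives no figure to reproduce, so the check sets the two rules side by side.

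**Inputs**
- Rule A (Section 7.1.1): resume if the stopping criterion is no longer met.
- Rule B (Section 7.1.1.2): restart if an alternative cause is definitively identified and values are back to pre-event levels.
- Liver state, three levels: criterion still met; below the stopping threshold but above the pre-event level; at the pre-event level.
- Alternative cause: found or not found.

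The middle liver state is needed because clearing a threshold and returning to pre-event values are different events. Take a participant with normal baseline tests, stopped for ALT above 8 × ULN, whose ALT falls to 4 × ULN with AST no higher, normal bilirubin and INR, and no symptoms or eosinophilia. Against the four normal-baseline conditions:
- above 8 × ULN: no;
- above 5 × ULN for more than two weeks: no;
- above 3 × ULN with raised bilirubin or INR: no, both are normal;
- above 3 × ULN with symptoms or eosinophilia: no.

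No listed condition is met, yet ALT is not at its pre-event level. The same state exists for raised-baseline participants: with a screening value below 2 × ULN, a fall from above 5 to 4 times that value, without symptoms or a bilirubin or INR rise, also clears every condition.

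**Result**

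| Liver state | Cause found | Rule A permits | Rule B conditions met | Same answer |
|---|---|---|---|---|
| Criterion still met | Yes | No | No | Yes |
| Criterion still met | No | No | No | Yes |
| Below threshold, above pre-event | Yes | Yes | No | **No** |
| Below threshold, above pre-event | No | Yes | No | **No** |
| At pre-event level | Yes | Yes | Yes | Yes |
| At pre-event level | No | Yes | No | **No** |

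The rules differ in 3 of 6 combinations, and in each of them Rule A is the more permissive.

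**Sensitivity to wording.** The middle rows take the criterion to mean the thresholds listed in Section 7.1.1.2. If it means any abnormal liver value, the middle state counts as still met and only the last row disagrees. The conflict does not disappear under either reading.

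**Bearing of the NOTE.** A normal-baseline participant stopped in line with the NOTE has already had other potential causes excluded. Rule B can then be satisfied only if later work-up identifies a cause, so the no-cause rows are the likely ones for this group.

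**Timing and reach.** Re-exposure would come at the next scheduled dose. Dosing days are 28 apart in the monthly phase (57 − 29) and 84 apart in the quarterly phase (421 − 337). The synopsis says "Up to a total number of 16 participants will be enrolled in Cohorts 1 and 2". At 3:1 within cohorts of 8, that is 2 × 8 × 3/4 = 12 on belcesiran and 16 − 12 = 4 on placebo.

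**The case against.** The best defence is structural. Section 7.1.1 reads as a general list followed by specific subsections, and a specific rule ordinarily prevails over a general one. Both sentences are permissive, so a site following Section 7.1.1.2 also complies with Section 7.1.1, and nothing compels re-dosing. This is a fair account of what was probably meant. It does not settle the text: the resume sentence expressly reaches every criterion above it, and the liver sentence says when restart is allowed, not that it is allowed only then.

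The second defence is that judgement fills the gap. Criterion 5, an Investigator safety concern, may keep a participant off drug after values normalise. Section 8 adds "Immediate safety concerns should be discussed with the Medical Monitor upon occurrence or awareness". The DSMC adjudicates potential stopping-rule events and decides on resumption, but by reference back to Section 7.1, where the conflict lies. The German rule in Section 10.5 makes Grade 4 events a permanent stop, subject to a baseline condition and only at German sites. These safeguards lower the chance of an unsafe restart, but none says which rule applies. A reader might therefore infer that Section 7.1.1 gives unrestricted re-dosing after DILI; the documents do not support that.

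A reader might also infer that the conflict is the expected outcome for any normal-baseline participant who recovers. That is too strong. The NOTE covers only the normal-baseline group; a stop can also follow from Investigator judgement of best interest or because close monitoring is impossible; and the required work-up (viral, autoimmune, ischaemic, biliary, environmental) may find a cause after the stop.

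**Conclusion.** The inconsistency is real and bears on safety. Read literally, Section 7.1.1 permits a restart in three situations where the conditions of Section 7.1.1.2 are unmet. The most serious is recovery from a possible DILI with no cause found. The count of 3 of 6 assumes that the criterion means the listed thresholds. It maps where the rules part and must not be read as a rate: no document says how often each combination would arise.

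The practical effect is limited. The SAP states that "the Sponsor made the decision to stop the trial prior to the enrollment of Cohort 3 subjects", which leaves the up to 16 planned participants of Cohorts 1 and 2. No endpoint or planned analysis depends on the point. A reader might infer that participants were re-exposed under the looser rule; nothing in the documents shows that any restart took place.

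**What to change.** Add an exception to the resume sentence in Section 7.1.1, so that it ends: *…except that for criterion 2 trial product may be restarted only if both conditions in Section 7.1.1.2 are met (alternative etiology definitively identified and liver blood parameters returned to pre-event levels).* Naming both conditions closes the intermediate state as well as the no-cause case.

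In the same edit, reconcile the normal-baseline NOTE with the restart rule by saying that a cause found in later work-up can satisfy the first condition. Otherwise restart looks almost unreachable for that group.

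The cost is one clause, plus the consequence that participants who recover without an identified cause remain off drug. Section 7.1.1.2 already intends that. With the trial stopped early, the change matters mainly for any dosing still under this text and for any later protocol that reuses it.
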